9. STUDY ENDPOINTS

9.1. The primary outcomes:

- **Efficacy endpoint**

- 1- Change in WHO Ordinal Scale for clinical improvement (baseline to end of study will be measured on days 1,7,14 and 28).

The World Health Organization (WHO-WHO) has proposed the “Ordinal Scale of Clinical Evaluation of the World Health Organization” presented below as a means of generating a numerical value to assess the health status of the participant to allow comparisons to be made in clinical studies. The scale is shown in the table below and will be used to assess a secondary effectiveness target in this study.

Patient State	Descriptor	Score
Uninfected	Uninfected; no clinical evidence and viral RNA detected	0
Ambulatory	Symptomatic; independent	1
	Symptomatic; assistance needed	2
Hospitalized: Moderate diseases	Hospitalized, no oxygen therapy	3
	Hospitalized; oxygen by mask or nasal prongs	4

	MGC Pharma Clinical Study Protocol	Protocol No.: MGC-009
		Version 02, 05 Sep 2021
		Page 34 of 76
A Phase IIb, double blind, placebo-controlled clinical study designed to evaluate the effect of CimetrA in patients diagnosed with COVID-19		CONFIDENTIAL

Hospitalized: Severe diseases	Hospitalized; oxygen by NIV or high flow	5
	Hospitalized; mechanical ventilation	6
	Mechanical ventilation and vasopressors, dialysis or ECMO	7
Dead	Dead	8

2- Change in COVID-19-Related Symptoms score (measured on days 1,7, 14, 28)

• **Safety Endpoints**

Safety will be assessed through collection and analysis of adverse events, blood and urine laboratory assessments and vital signs.

9.2. **The secondary outcomes:**

- Number of participants with depending on oxygen supplementation through day 28 since onset of symptoms
- Change in inflammatory marker levels - IL-6, IL-1 β , IL-12, TNF α , IFN- γ , CRP, NLR (Neutrophil / Lymphocyte ratio) (days 1, 2, 4, 7) compared to baseline
- Pharmacokinetic profile of the study drug on day 1 through 24 Hrs.
- Incidence and duration of mechanical ventilation
- Incidence of Intensive Care Unit (ICU) stay during COVID-19 complication
- Percentage of participants with definite or probable drug related adverse events
- Long term adverse events of COVID-19 on Day 28
- The Impact covid_19 on quality of life of patients on Days 1, 14 and 28

9.3. **The exploratory outcomes:**

- Course of change in D Dimer levels compared to baseline

	MGC Pharma Clinical Study Protocol	Protocol No.: MGC-009
		Version 02, 05 Sep 2021
		Page 35 of 76

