12.2. Packaging and Labelling of Study Products

CimetrA-1, CimetrA-2 and Placebo is supplied in a bottle containing 5 ml.

The Product is packed in a bottles with a spray pump. It is administered by spraying into the oral cavity.

bottles are closed with a validated spray delivery system , Spray pump on product bottle enables dosing 0.2 ml of CimetrA-1 /0.14 ml of CimetrA-2 in each press and will be packaged and labelled in compliance with the GMP, and EU regulation regarding drugs used in clinical trials.

The lot number and date of manufacture for the clinical lot used in the study will be provided to the clinical site and will be reported in the Clinical Study Report. The documentation supplied by the Sponsor for the study medication (i.e. Certificate of

	MGC Pharma Clinical Study Protocol	Protocol No.: MGC-009
		Version 02, 05 Sep 2021
		Page 51 of 76
A Phase IIb, double blind, placebo-controlled clinical study designed to evaluate the effect of CimetrA in patients diagnosed with COVID-19		CONFIDENTIAL

Analysis for the test product) will make it possible to retrace the composition and pharmaceutical profiles of the test product .

Study Product will be labeled with :

- Product name
- Dose
- Lot number
- Date of manufacture
- Protocol number
- Sponsor's name
- Instructions for use and storage
- "Investigational Use Only" statement

Placebo will be administrated in the same way, and will be identical in its characteristics to the study drug in order to prevent bias.

12.3. **Storage, Dispensing and Return of the Investigational product**

Bottles containing the study product should be stored at room temperature. Records should also be kept by the Investigator or pharmacist as to how much study drug was used by each subject. The study monitors must check during each visit the study drug supplied to ensure expiry date and sufficient amount of study drug. All investigational products must be kept in a locked area with access to the study drug limited to designated study personnel. Only personnel under the supervision of either the Investigator or the local pharmacist are authorized to dispense study drug. During storage at the pharmacy, the temperature will be monitored and recorded by a pharmacist or a temperature log. The Sponsor will be notified for any deviation from the storage conditions.

	MGC Pharma Clinical Study Protocol	Protocol No.: MGC-009
		Version 02, 05 Sep 2021
		Page 52 of 76

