A Phase IIb, double blind, placebo-controlled clinical study designed to evaluate the effect of CimetrA in patients diagnosed with COVID-19		CONFIDENTIAL

12.4. **Accountability and Compliance**

Each delivery must be acknowledged by the pharmacist (or authorized study team member responsible for the investigational medicinal product) by filling in the receipt record form. The study staff will confirm the receipt of clinical supply and will return signed drug accountability logs to the study monitor.

The pharmacist (or authorized study team member responsible for the investigational medicinal product) are responsible for ensuring the supervision of the storage and allocation of these supplies, which will be forwarded to the Investigator at the appropriate time before administration. The Investigator or pharmacist may dispense investigational drug only to subjects enrolled in the study. Treatment compliance will be assessed at all visits during the Treatment Period. It will be based on drug accountability (volume measure), and subject's diary review. Study drug compliance may be enhanced with regular telephone and other reminders. Drug accountability records must be maintained by the clinical investigation site at all times. At the last study visit, all used and unused investigational drug will be assessed for accountability by the study monitor. The subject identification number, the date, batch number/pack number, and quantity of study drug used by the subject will be checked for correctness and recorded on the appropriate accountability forms. Unused drug supplies will be returned to the Sponsor. At the end of the study, all the clinical supply and the corresponding accountability forms must be returned by the study monitor for reconciliation and destruction. A copy of these records must be kept at the clinical investigation site.

The inventory will be made available to the study monitor who will verify accountability and verify dose during the course of the study. Study drug orders, records of study drug receipts, dispensing records, and inventory forms located at

	MGC Pharma Clinical Study Protocol	Protocol No.: MGC-009
		Version 02, 05 Sep 2021
		Page 53 of 76
A Phase IIb, double blind, placebo-controlled clinical study designed to evaluate the effect of Cimetra in patients diagnosed with COVID-19		CONFIDENTIAL

the site will be examined and reconciled by the study monitor periodically during and at the end of the study.

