It is important to say that both active ingredients of the study drug is defined as GRAS and found to be safe with no adverse events in clinical studies. Based on the literature, the following data regarding the potential risks of the Curcumin and Boswellia is available –

1. Madhu K at al., Rahmani et al. and Selvi et al. reported gastrointestinal adverse events related to diarrhea, nausea and abdominal pain
2. Chuengsamarn et al. reported hot flashes and constipation that were observed in the clinical trial in type 2 diabetes patients .

14. **ADVERSE EVENT**

14.1. **Definition of adverse event**

Adverse event means any untoward medical occurrence associated with the use of a drug in

	MGC Pharma Clinical Study Protocol	Protocol No.: MGC-009
		Version 02, 05 Sep 2021
		Page 55 of 76
A Phase IIb, double blind, placebo-controlled clinical study designed to evaluate the effect of Cimetra in patients diagnosed with COVID-19		CONFIDENTIAL

humans, whether or not considered drug related.

An Adverse Event (AE) is any untoward medical occurrence in a subject administered a pharmaceutical product, whether it is related to the pharmaceutical product in question or not. This includes a change in a subject's condition or laboratory results, which has or could have a deleterious effect on the subject's health or well-being.'

In this study, local reactions due to study treatment will be captured in the diary, and this information will not be duplicated in the CRFs.

AEs to be recorded in the CRFs are systemic reactions that also are captured in the diary and other AEs occurring that are not due to study treatment.

14.2. **Methods for eliciting AEs**

All subjects should be carefully monitored for occurrence of AEs during the study and for a reasonable time period thereafter. No distinction should be made between the investigational treatment and the placebo treatment for the purpose of AE reporting.

All directly observed and spontaneously reported AEs should be recorded in the CRF. If no AE has occurred during the study period, this should also be recorded in the CRF. In addition, each study subject will be asked an open question about possible AEs at each clinic visit following initiation of treatment.

The following evaluations are to be done by the Investigator in connection with the AE:

- type of event
- seriousness
- degree of severity
- duration (start - end)
- action taken

	MGC Pharma Clinical Study Protocol	Protocol No.: MGC-009

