Sample size and Power were calculated with the Power and Precision statistic program ver 4.1 and all statistical analyses and data presentations, including tabulations and listings, will be performed using the SPSS statistic program version 27.0 (or higher) software.

Randomization

Randomization tend to produce study groups comparable with respect to known and unknown risk factors, removed investigator bias in the allocation of participants and guarantees that statistical tests will have valid false positive error rates.

After a participant will meet the eligibility criteria, he/she will be randomly allocated (with a 1:1:1 ratio) to one of the following treatment groups based on a randomization scheme stratified by center.

The randomization scheme will be prepared by an independent statistician using statistic program for random number generator. The block size is set in ahead and study personnel will be blinded to the randomization block size.

Blinding

This is a double-blind study: neither the participants nor the investigators will be aware of arm allocation of each study participant.

Blindness is important to avoid bias. Monitoring and reporting of the success of blindness are important for the reader's confidence of the trial results. Groups should be marked by capital letter and blindness should maintain throughout the study.

Missing Data

Safety data should be collected from non-adherent/withdrawal participants to avoid possible bias.

	MGC Pharma Clinical Study Protocol	Protocol No.: MGC-009
		Version 02, 05 Sep 2021
		Page 62 of 76
A Phase IIb, double blind, placebo-controlled clinical study designed to evaluate the effect of Cimetra in patients diagnosed with COVID-19		CONFIDENTIAL

Prior to analyzing the data, extreme laboratory values should be checked. Missing values will be treated as ITT.

Multiple imputation for binary data will be used as the primary imputation method in the case of missing data for the primary efficacy endpoint.

Dropout/AE Imputation: A participant with no post baseline measurement or a participant withdrawn due to an adverse event or treatment intolerability will use last observation carried forward imputation methods.

Baseline Data

Baseline participant characteristics will be collected at screening. The specific baseline (“start of treatment”) endpoints and other symptoms will be collected prior to each treatment.

Significance Levels and Handling of Type I Error

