The overall significance level for this study is 5% using two-tailed tests, except for treatment by center/region interaction that will be tested at a significance level of 10%.

When multiple comparisons between the groups are made, the chance of finding a significant difference in one of the comparisons is greater than the stated significance level, therefore we will use pot-hoc analysis.

Efficacy endpoints:

Time to sustained clinical improvement (as defined earlier).

Safety Endpoints

The safety endpoints of adverse events and tolerability will be assessed by review of all safety parameters, including adverse events.

	MGC Pharma Clinical Study Protocol	Protocol No.: MGC-009
		Version 02, 05 Sep 2021
		Page 63 of 76
A Phase IIb, double blind, placebo-controlled clinical study designed to evaluate the effect of CimetrA in patients diagnosed with COVID-19		CONFIDENTIAL

The incidence of adverse events will be assessed as a function of severity and association to the device. The time of resolution of the adverse events and need for treatment will also be analyzed.

Analysis Sets

The ITT analysis set will serve as the main set for safety assessments.

The primary and secondary performance efficacy assessments will also be performed on the PP and the ITT analysis sets.

Statistical Analysis

Demographic and Baseline

Demographic and baseline condition related characteristics will be tabulated and compared between the study arms by data type. Continuous variables will be summarized by a mean, standard deviation, minimum, median and maximum and categorical variables by a count and percentage.

Primary Efficacy Analysis

The primary efficacy endpoint of the study is the mean change in the WHO Ordinal Scale. It will be evaluated using a General Linear Model ANOVA test.

Subset Analyses

The primary endpoint will also be evaluated stratified by center using a General Linear Model ANOVA test.

A sensitivity analysis of the primary endpoint will be performed to assess the impact of missing data on the study outcome.

Adjustment for other covariates such as demographics or other baseline participant characteristics may be performed by adding these variables into a multivariate linear regression.

Secondary Efficacy Analysis

	MGC Pharma Clinical Study Protocol	Protocol No.: MGC-009
		Version 02, 05 Sep 2021
		Page 64 of 76

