A Phase IIb, double blind, placebo-controlled clinical study designed to evaluate the effect of CimetrA in patients diagnosed with COVID-19		CONFIDENTIAL

The 3 groups will be compared with the ANOVA test or Kruskal Wallis non-parametric test, following by post-hoc analysis for pairs differences.

Additional Efficacy Parameters of Interest

A count and percentage of participants responding to each of the exploratory efficacy endpoints will be presented. The groups will be compared with a chi-squared test or a Fisher’s exact test.

Safety Analysis

The primary safety variable, the cumulative incidence (and 95% CI) of device related adverse events (AEs) throughout the study, will be presented in tabular format and will include incidence tables by severity.

Serious adverse events, device-related SAEs, adverse events (by type and overall), device-related AE, adverse device reactions and device malfunction rates will be compared between the study arms with a Fisher’s exact test.

Serious adverse events will be listed and discussed individually.

PK test

Actual times of dosing and blood collection at various time points will be recorded in source documents as well as CRF’s. Objectives of PK sampling are to measure values of CimetrA active ingredients in plasma at different time point after first administration of study medications and at different time point after multiple administrations during steady state.

PK samples will be processed and frozen on site. Labels have been prepared for the site again containing patient No., visit No., type of test (PK) and time point. Upon completion of the study, samples will be sent to selected analytical laboratory with dedicated courier service. The PK parameters will be obtained from plasma concentration data for curcumin and boswellia.

	MGC Pharma Clinical Study Protocol	Protocol No.: MGC-009
		Version 02, 05 Sep 2021
		Page 65 of 76
A Phase IIb, double blind, placebo-controlled clinical study designed to evaluate the effect of Cimetra in patients diagnosed with COVID-19		CONFIDENTIAL

Analyses of PK data will be based on the PK Set, which will include all subjects who received at least one treatment and for whom concentration data is available.

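### Protocol section 17 makes ITT the main safety set and names no set of dosed patients grouped by the product they received

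*Protocol*

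**What the plan says.** Section 17, Analysis Sets, fixes the population for safety: "The ITT analysis set will serve as the main set for safety assessments". Efficacy is to be assessed on both the PP and the ITT sets. ITT is not defined. Its only other use is a remark on missing values in the same section.

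The one set that depends on dosing is in the PK test part of section 17: "Analyses of PK data will be based on the PK Set, which will include all subjects who received at least one treatment". It serves the pharmacokinetic analysis only. No safety set, as-treated set or rule on product received appears in the protocol as shown.

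The choice of set bears on two safety measures:

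- Section 17, Safety Analysis: "The primary safety variable, the cumulative incidence (and 95% CI) of device related adverse events (AEs) throughout the study". The product is a spray, so I read device-related here as treatment-related.
- Section 9.2: "Percentage of participants with definite or probable drug related adverse events".

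Section 14.1 ties an AE to exposure: "An Adverse Event (AE) is any untoward medical occurrence in a subject administered a pharmaceutical product".

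**The concern.** Analysing patients as randomised protects the efficacy comparison. The safety question is what happened to people exposed to a given product. Using ITT as the main safety set has two consequences.

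1. **Wrong product.** An AE in a patient given the wrong bottle is tabulated under the randomised arm. Active-placebo errors then pull the AE difference towards zero, which is the unsafe direction for a safety analysis. Errors between the two doses blur the dose comparison.
2. **Never dosed.** A randomised patient who received no spray cannot, under section 14.1, contribute a treatment-related AE, yet counts in the denominator. This lowers the incidence and the upper limit of its 95% CI in that arm. Where it happens in the placebo arm it can widen the active-placebo contrast, so the direction does not always favour the drug.

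This is not a detail left to the SAP, because the protocol itself selects the main safety set. Safety also stands among the primary outcomes in section 9.1.

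**Working it through.** The protocol gives no figure for dosing errors or never-dosed patients, so there is no planned number to reproduce. What follows shows how the size depends on assumed counts.

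**Inputs**

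- From section 17: 80 patients per arm, three arms, 240 in total.
- Assumed: *m* affected patients per arm, with *m* = 1 (3 in 240), 2, or 4 (12 in 240, or 5%; a high case). Write *e* = *m*/80.
- Assumed: true AE rates of 15% (high dose), 10% (low dose) and 5% (placebo).

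**1. Wrong bottles, all between active and placebo, with the placebo arm's errors split evenly between the two doses**

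The rates reported by randomised arm are:

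- high = (1 − e)·15 + e·5
- low = (1 − e)·10 + e·5
- placebo = (1 − e)·5 + e·(15 + 10)/2

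For *m* = 4 (*e* = 0.05) these are 14.5%, 9.75% and 5.375%. The differences from placebo, in percentage points, are:

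| Contrast | True | m = 1 | m = 2 | m = 4 |
|---|---|---|---|---|
| Pooled active − placebo | 7.5 | 7.31 (−2.5%) | 7.125 (−5%) | 6.75 (−10%) |
| High dose − placebo | 10 | 9.78 (−2.2%) | 9.56 (−4.4%) | 9.125 (−8.75%) |
| Low dose − placebo | 5 | 4.84 (−3.1%) | 4.69 (−6.25%) | 4.375 (−12.5%) |

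Under this even split the pooled difference scales by 1 − 2e whatever the rates. The single-dose figures depend on the assumed rates and on where the placebo errors fall.

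**2. Wrong bottles spread evenly over the other two arms**

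Every pairwise difference scales by 1 − 1.5e, for any rates: −1.9%, −3.75% and −7.5% for *m* = 1, 2 and 4.

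**3. Swaps between the two doses only**

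The dose difference scales by 1 − 2e. Pooled active minus placebo stays at 7.5 points.

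**4. Never-dosed patients**

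The treatment-related incidence in the arm is multiplied by (80 − m)/80, that is 0.9875, 0.975 and 0.95. The upper limits are Clopper-Pearson, two-sided 95%, with no events: 1 − 0.025^(1/n).

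| Denominator | Incidence with 4 events | Upper limit with 0 events |
|---|---|---|
| 80 (ITT) | 5.00% | 4.51% |
| 79 dosed (m = 1) | 5.06% | 4.56% |
| 78 dosed (m = 2) | 5.13% | 4.62% |
| 76 dosed (m = 4) | 5.26% | 4.74% |

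With *m* = 0 every effect is nil.

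**The case against.** The strongest reply is that both consequences rest on a definition of ITT that the protocol does not give, and that the SAP could supply. Calling ITT the main set also leaves room for a supporting as-received table. This stands in part. If ITT were defined as dosed patients only, the never-dosed point would disappear. The wrong-bottle point would remain, because patients would still be grouped as randomised.

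The second reply concerns size, and it largely stands:

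- Patients are in hospital, and randomisation and first dose both fall on day 1.
- Bottle changes should be rare: "CimetrA-1, CimetrA-2 and Placebo is supplied in a bottle containing 5 ml", and the full course needs 4 × 1 ml = 4 ml or 4 × 0.7 ml = 2.8 ml.
- Section 12.4 requires that "batch number/pack number, and quantity of study drug used by the subject will be checked for correctness".
- Section 11.3(a) classes patients found ineligible at the initial assessments as not enrolled. This may remove one route to being randomised but never dosed, although the text does not fix the order of events.
- Section 13.3 reports no drug-related AEs in the 50-patient study of the earlier formulation. Without a true difference, swaps have nothing to shrink.
- In the high case the losses for the single doses are 0.875 and 0.625 percentage points, each under one patient in 80. The Wald 95% half-width for 15% against 5% is 1.96·√(0.15·0.85/80 + 0.05·0.95/80) ≈ 9 points.
- SAEs are also discussed one by one, which limits masking of serious events.

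The third reply is that ITT keeps withdrawn patients, in line with the Missing Data text: "Safety data should be collected from non-adherent/withdrawal participants to avoid possible bias". This does not rescue the choice, because a dosed, as-received set keeps every treated withdrawal too.

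**Conclusion.** The concern holds, at minor severity. The protocol fixes ITT as its main safety set and offers no dosed, as-received alternative, although its own AE definition presupposes exposure.

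The conclusion assumes the ordinary meaning of ITT. The sizes rest on assumed error counts and AE rates. They are small in absolute terms, and no planned Fisher comparison is shown to change its result. Wrong bottles between active and placebo reduce the apparent harm of the drug. The effect of never-dosed patients depends on the arm in which they fall.

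**What to change.** Replace the sentence on the safety set in section 17 with:

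> The main set for safety assessments is all randomised patients who received at least one dose of study product, analysed by the product actually received; a patient who received more than one product is assigned to the highest active dose received.

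Assign the product from the batch, pack and quantity records kept under section 12.4. Keep ITT for efficacy.

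The cost is one sentence. It needs no extra patients, procedures or data, and the sample size and power are untouched. There are two small drawbacks. The safety comparison is no longer strictly as randomised, and a patient given both placebo and active has all AEs counted under active, which is the cautious direction.

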17. STATISTICAL METHODS AND DETERMINATION OF SAMPLE SIZE

A prospective, randomized (1:1:1), double-blind, multi-center, placebo-controlled clinical study.

Statistical Hypothesis

The hypothesis of this study is that treating with CimetrA and CimetrA2 will be more effective, while maintaining a favorable safety profile. This will be demonstrated by a significant difference between the two active and the control groups.

	MGC Pharma Clinical Study Protocol	Protocol No.: MGC-009
		Version 02, 05 Sep 2021
		Page 60 of 76
A Phase IIb, double blind, placebo-controlled clinical study designed to evaluate the effect of Cimetra in patients diagnosed with COVID-19		CONFIDENTIAL

In this study, we will test the following hypothesis:

- H0: $\Delta_1 = \Delta_2 = \Delta_3$
- H1: at least one is different.

Where Delta is the difference between baseline and end of study in WHO Ordinal Scale for clinical trial.

If the null hypothesis is rejected in favor of the alternative hypothesis the study will be deemed successful.

Safety will be assessed by adverse events, blood and urine laboratory assessments and vital signs.

Planned Sample Size

For this phase IIb, 3-armed clinical trial, we use the ANOVA test to estimate the expected improvement in the primary outcome; the WHO ordinal scale for clinical improvement.

We expect medium effect ($f=0.20$) for the differences in Delta between the 3 groups, and standard deviation of 1.5, based on the ordinal scale (0-8). This power analysis is for a one-way fixed effects analysis of variance with 3 levels. The study will include 80 patients per group for a total of 240 patients.

The criterion for significance (α) has been set at 0.05 with Power of at least 80%.

The analysis of variance is two-tailed Main effects.

For immunogenicity assessment, larger sample size will reduce mean variability in the observed outcomes and will increase the opportunity to detect real changes.

For 80 participants per group we ensure the desired precision for phase 3 trial to assess safety and effectiveness. Total sample 240 patients.

Computer Software

	MGC Pharma Clinical Study Protocol	Protocol No.: MGC-009
		Version 02, 05 Sep 2021
		Page 61 of 76
A Phase IIb, double blind, placebo-controlled clinical study designed to evaluate the effect of CimetrA in patients diagnosed with COVID-19		CONFIDENTIAL

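### The primary efficacy test is planned on both the PP and the ITT set, and the protocol does not say which of them decides whether the study succeeded

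*Protocol*

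**What the plan says.** All references are to the protocol.

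- **Section 17, Statistical Hypothesis.** The null hypothesis is that the mean change in the WHO ordinal scale is the same in the three arms. The success rule is "If the null hypothesis is rejected in favor of the alternative hypothesis the study will be deemed successful". No analysis set is attached to it.
- **Section 17, Analysis Sets.** "The ITT analysis set will serve as the main set for safety assessments". For efficacy, "The primary and secondary performance efficacy assessments will also be performed on the PP and the ITT analysis sets". The two sets are not ranked, and agreement between them is not required.
- **Section 17, Primary Efficacy Analysis.** The test is a general linear model ANOVA. No set is named.
- **Section 17, Significance Levels.** "The overall significance level for this study is 5% using two-tailed tests". The only remark on multiplicity concerns comparisons between groups.
- **Section 17, Missing Data.** Missing values are to be handled on an ITT basis, with multiple imputation for the primary endpoint and last observation carried forward for some withdrawals and for participants with no post-baseline value.
- **Section 11.3 b to f.** Subjects removed or withdrawn, including non-compliers and treatment failures, are kept out of the primary analyses. Item c makes an exception for removal on safety grounds.

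**The concern.** The success rule turns on one rejection of one null hypothesis, but the protocol plans to test that hypothesis on two overlapping sets of patients and does not say which test counts. Where the two disagree, the text gives no means of deciding.

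The two sets are not equivalent. ITT keeps the comparison that randomisation created. PP is selected afterwards, and if it follows section 11.3 it loses treatment failures and non-compliers, who may differ between arms because of treatment. A PP result quoted as the study's success would not be a fully randomised comparison. Conversely, a positive ITT result could be challenged by a negative PP result with nothing in the protocol to answer the challenge.

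**Working it through.** **1. The plan's own figure.** Inputs from section 17: f = 0.20, three groups, 80 per group (N = 240), "The criterion for significance (α) has been set at 0.05 with Power of at least 80" per cent, and "This power analysis is for a one-way fixed effects analysis of variance with 3 levels". The noncentrality is λ = N·f² = 240 × 0.04 = 9.6, and the critical value of F(2, 237) at 0.05 is 3.034. Power = P(noncentral F(2, 237; 9.6) > 3.034) = 79.3%. Reaching 80% needs 82 per group (246 in total), which gives 80.4%. The stated size therefore reproduces to within rounding, falling just short of 80%, and it includes no allowance for exclusions.

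**2. Power if PP were decisive.** The protocol gives no PP share. Assume 10%, 20% or 30% of each arm is outside PP and apply the same formula:

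| Outside PP | PP per arm | λ = 3n × 0.04 | Power |
|---|---|---|---|
| 0% (ITT) | 80 | 9.60 | 79.3% |
| 10% | 72 | 8.64 | 74.6% |
| 20% | 64 | 7.68 | 69.1% |
| 30% | 56 | 6.72 | 62.8% |

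**3. Type I error if success on either set were accepted.** Simulation: three arms of 80, normal outcome, no treatment effect, PP a random subset of ITT, one-way F test at 0.05 on each set, 200,000 trials per row (Monte Carlo standard error about 0.05 percentage points).

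| Outside PP | One named set | Either set |
|---|---|---|
| 10% | 5.0% | 6.5% |
| 20% | 5.0% | 7.2% |
| 30% | 5.0% | 7.6% |

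The inflation stays below the Bonferroni bound of 0.05 + 0.05 = 10% because the sets overlap heavily.

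**4. Disagreement at the planned effect.** Same simulation with f = 0.20 and equally spaced means:

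| Outside PP | ITT only significant | PP only significant | Total |
|---|---|---|---|
| 10% | 6.9% | 2.1% | 9.0% |
| 20% | 12.5% | 2.4% | 14.9% |
| 30% | 18.9% | 2.4% | 21.3% |

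Placing one arm apart from two equal arms, at the same f, gives almost the same figures.

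**5. Whether other text names the set.** The missing-data rules make most sense if all randomised patients are kept, which points to ITT. Section 11.3 b to f points to a PP-like set. Neither names a decisive set, and they conflict.

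**The case against.** **This belongs in the SAP.** Definitions of analysis sets, and often their ranking, are commonly left to the SAP, and running efficacy on both sets is routine. That would be a full answer if the protocol were silent. It is not: it fixes the success rule and the overall alpha, ranks the sets for safety but not for efficacy, and contains two passages that imply different primary populations. An SAP would have to override one of them.

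**The protocol does not permit success on either set.** A reader might infer that it sets up two full-alpha primary tests and lets the sponsor claim success on whichever is significant. No passage says so. There is one null hypothesis, one primary analysis paragraph and one overall 5% level. This objection stands: the supportable statement is that the decisive set is not named. The 6.5% to 7.6% is what an either-set reading would cost, not the plan's stated error rate.

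**Most disagreement is harmless.** A reader might also take the total disagreement of 9% to 21% as the size of the problem. It is not. Most of it is ITT significant and PP not, which reflects the smaller PP set and which an ITT-decisive rule would also count as success. Under random exclusion, PP-only success is about 2% to 2.5%.

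**Few patients may be excluded.** Treatment is four spray doses over two days in inpatients, so missed doses alone are unlikely to remove 20% to 30%. This is fair, but the removal rules in section 11.3 reach well beyond dosing.

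**Conclusion.** The point holds as an ambiguity about the trial's only success criterion. Section 17 does not say which set decides, and section 11.3 and the missing-data text pull in opposite directions.

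The numerical effect is moderate. An either-set reading would raise type I error from 5% to between 6.5% and 7.6%. A PP-decisive reading would cut power from 79% to between 75% and 63%. Both ranges rest on an assumed 10% to 30% outside PP, excluded at random, with a normally distributed outcome.

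Random exclusion is the favourable case. Treatment failures and non-compliers are not a random subset, and leaving them out could bias the comparison in a direction and by an amount that the documents do not allow one to compute. The documents do not show an intention to choose the set after seeing the results; they only fail to rule it out. The correction should be made before unblinding.

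**What to change.** In section 17, replace the efficacy sentence under Analysis Sets with text to this effect: the primary efficacy test and the declaration of study success use the ITT set, meaning all randomised patients in the arm assigned; the PP analysis is supportive and cannot by itself establish success; the same order applies to the secondary outcomes.

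This does not work alone. Section 11.3 b to f would still bar the removed subjects from the primary analyses and would contradict an all-randomised primary set. Reword those items so that the subjects concerned are left out of the PP set only. This concerns how their data are analysed, not when treatment or participation should stop.

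**Cost.** Text changes in two sections and no additional patients. Success could no longer be claimed from PP alone. Subjects who leave the study early would enter the primary analysis through whatever later WHO scores are collected and otherwise through imputation, so the missing-data rules carry more weight.
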